After general anesthesia induction, our newly designed TEE probe cover (FIGURE 1; Fuji Medical, Tokyo, Japan) was attached to the X7 TEE probe (Philips Medical Systems, Andover, MA) and inserted into the patient's esophagus, and an OG tube (Salem Sump nasogastric tube, 16 Fr., Covidien, Minneapolis, MN) was advanced through the second lumen of the TEE probe cover. The length of advanced OG tube was adjusted so that the tip of OG tube would be 2-3 cm out of the second lumen. TEE images were intraoperatively collected by National Board of Echocardiography (NBE)-certified advanced

perioperative echocardiographers, who are blinded to this study design, using an iE33 echocardiographic machine (Philips Medical Systems, Andover, MA) and stored in Syngo Workflow (Siemens Medical Solution, Malvern, PA, USA). The designated views for TEE images were as follows: midesophageal 4-chamber view (ME4C), midesophageal 2-chamber view (ME2C), midesophageal aortic valve short-axis view (ME AV SAX), midesophageal long-axis view (ME LAX), midesophageal bicaval view (ME BIC), transgastric midpapillary short-axis view (TG Mid SAX), and deep transgastric long-axis view (DTG LAX). Image acquisition was performed twice, before and after OG tube suctioning, when the baseline TEE assessment was performed after general anesthesia induction. Suction was performed for 1 minute at > -110 cm H₂O, and the amount and characteristics of the suctioned content were recorded. While acquiring these views, the TEE device setting was not changed, and the iSCAN button was pressed before video acquisition.¹⁰⁻¹³

Image quality assessment

TEE image quality was assessed in 2 different ways based on the TEE images acquired before and after suctioning. In the first method (method #1), the investigators categorized the quality of all acquired images on a numeric scale based on each investigator's impression (1: very poor, 2: poor, 3: acceptable, 4: good, and 5: very good). In the second method (method #2), the reproducibility of the LV FAC and right ventricular fraction area change (RV FAC) was assessed, assuming that better TG Mid SAX and ME4C image quality would yield better LV FAC and RV FAC reproducibility, respectively.¹⁸ LV FAC was calculated using TG Mid SAX, while RV FAC was calculated using ME4C.

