Three investigators (A, B, and C), who were also NBE-certified advanced perioperative echocardiographers, assessed the quality of all TEE images post hoc. Thus, 50 x 3 sets of images for each were evaluated to determine the interobserver variability. Subsequently, following an interval of between 6 and 8 months, investigator C again analyzed all images to determine the intraobserver variability. To minimize selection bias, all investigators were blinded to the hypothesis of the study. Additionally, all investigators were blinded to which images were obtained before or after suctioning.

Outcomes

The quality of images obtained before and after pinpoint suctioning with our newly designed TEE probe cover was assessed using the following views: ME4C, ME2C, ME AV SAX, ME LAX, ME BIC, TG Mid SAX, and DTG LAX. As described in method #1, post hoc assessments were performed using image quality

categorized as discrete numbers based on each investigator's impression (1: very poor, 2: poor, 3: acceptable, 4: good, and 5: very good) before and after suctioning. Image quality improvement was defined as an increase in this number. Additionally, as described in method #2, the LV FAC was also assessed post hoc for intraclass correlation coefficient (ICC) analysis. Furthermore, we assessed the occurrence of TEE probe-related complications (postoperative severe sore throat, dysphagia, bloody aspirate from the OG tube) and the suctioned volume.

Statistical Analysis

Continuous variables with a normal distribution are displayed as the mean \pm standard deviation, while those variables with a nonnormal distribution are displayed as the median and interquartile range. Categorical variables are presented as proportions and absolute numbers. For continuous variables, normality was tested using the Kolmogorov-Smirnov test.

The differences between 2 groups were investigated using the chi-square test or Fisher's exact test if any of the expected frequencies were <5 for categorical variables and unpaired and paired Student's ttests or the Mann-Whitney U test for continuous variables. Differences among 3 groups were investigated using Fisher's exact test for categorical variables and one-way ANOVA or the Kruskal-Wallis test for continuous variables.

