Intraobserver and interobserver reliability analyses of the LV FAC and RV FAC were performed using the ICC20-22. We obtained consistency ICCs for interobserver variability using all three investigators and absolute-agreement ICCs for intraobserver variability using investigator C, who measured all images twice at an interval between 6 and 8 months. The proportion of cases showing improvement using the numeric scale and the occurrence of TEE probe-related complications (severe sore throat, dysphagia, and bloody aspirate from the OG tube) are also reported for descriptive assessment. The change in image quality according to the numeric scale (method #1) was averaged for the same case, and its association with the suctioned volume was assessed using Pearson's or Spearman's rank correlation test. All statistical analyses were performed with R (version 4.0.2). A p-value of less than 0.05 was considered statistically significant.

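### Method #2 measures FAC reproducibility only by the ICC, which counts image error shared by all readers as between-patient variance, so it can stay flat or fall when images improve

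*Combined protocol and SAP*

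**What the plan says.** Under Image quality assessment, Method #2 assesses the reproducibility of LV FAC and RV FAC, "assuming that better TG Mid SAX and ME4C image quality would yield better LV FAC and RV FAC reproducibility, respectively". Two acquisitions per patient are compared. Data Collection states: "Image acquisition was performed twice, before and after OG tube suctioning".

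Three investigators "assessed the quality of all TEE images post hoc", so each of them measures the same stored clip. The number of sets is given as "50 x 3 sets of images for each were evaluated to determine the interobserver variability". I take this as 50 patients at each time point.

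The Statistical Analysis section then says: "Intraobserver and interobserver reliability analyses of the LV FAC and RV FAC were performed using the ICC20-22". The two forms are:

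- Between readers: "We obtained consistency ICCs for interobserver variability using all three investigators".
- Within reader: "absolute-agreement ICCs for intraobserver variability using investigator C, who measured all images twice", 6 to 8 months apart.

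No other measure of reproducibility is named: no standard error of measurement, limits of agreement or variance components. There is no reference value of FAC. The section sets a general significance level ("A p-value of less than 0.05 was considered statistically significant") but gives no test or interval for the change in ICC.

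**The concern.** An ICC is a ratio: between-patient variance over between-patient variance plus reading error. It bears on suctioning only through its change from before to after. Each patient contributes one image per view and time point, read by everyone, so the ICC cannot separate a true difference in FAC from an error in the image that pushes all readers the same way. If such error varies between patients, it goes into the numerator. This applies to both ICC forms, because investigator C's repeat readings are also of the same clips.

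Poor images can plausibly cause error of this kind, so the measure may give credit for part of the defect that suctioning is meant to remove. What is at stake is whether Method #2 can support the impression scores of Method #1. A flat or lower ICC could be reported as no gain in reproducibility when reader error had in fact fallen.

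**Working it through.** The plan gives no ICC, FAC SD or reader error, so there is no figure to reproduce. From the documents come 50 image sets, 3 readers, 2 readings by investigator C, and the ICC types. Every variance below is an assumption.

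**Model.** Reading = true FAC (SD T) + image error shared by all readings of that image (SD A) + reader error (SD e). Then

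ICC = (T² + A² + 2cov) / (T² + A² + 2cov + e²),

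where cov is the covariance of shared error with true FAC.

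**Example 1.** T² = 75; A² = 25 before and 0 after; cov = 0.

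- Before, e² = 25: 100/125 = 0.80.
- After, e² still 25: 75/100 = 0.75. The ICC falls although all shared error is gone.
- After, e² = 18.75 (SD 4.33): 75/93.75 = 0.80. The ICC is unchanged, while reader SD falls by 1 − 4.33/5.0 = 13%.

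**Break-even.** With A removed and cov = 0, the ICC falls unless e after is below e before × T/√(T² + A²). For T = 10, reader error must drop by more than 4% (A = 3), 11% (A = 5), 18% (A = 7) or 29% (A = 10).

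**Sampling check.** Simulation with 50 patients, 3 readers, T = 10, A = 0 after suctioning, shared error independent of true FAC, no systematic reader differences, and 4,000 replicates:

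| A before | e before → after | Theoretical ICC before → after | Chance that the after ICC is lower |
|---|---|---|---|
| 0 | 6 → 5.5 | 0.735 → 0.768 | 25% |
| 7 | 6 → 6 | 0.805 → 0.735 | 90% |
| 7 | 6 → 5.5 | 0.805 → 0.768 | 76% |
| 7 | 6 → 5 | 0.805 → 0.800 | 53% |
| 7 | 6 → 4.5 | 0.805 → 0.832 | 28% |
| 7 | 6 → 4 | 0.805 → 0.862 | 8% |
| 10 | 6 → 5 | 0.847 → 0.800 | 86% |

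For two readings by one reader, A = 7 and e from 6 to 5.5, the chance is 72%. The 25% in the first row is sampling error alone.

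**Where the direction changes.**

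- A shift equal in every patient adds no variance and leaves the ICC as it was.
- Shared error raises the ICC only if A² + 2cov > 0. In Example 1 the sign flips at a correlation of −25/(2 × 8.66 × 5) = −0.29. At −0.5 the shared-error term gives 75 + 25 − 43.3 = 56.7, so the ICC is 56.7/81.7 = 0.69 before and 0.75 after: it rises.
- An artefact that compresses readings therefore lowers the ICC. With T = 10, A = 7 and e = 6, a correlation of −0.5 gives 79/115 = 0.687 and −0.7 gives 51/87 = 0.586, against 100/136 = 0.735 with no artefact.

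**The case against.** The strongest reply is that the within-image SD does no better on shared error. In Example 1 with e² fixed at 25, it is 5.0 before and 5.0 after, a ratio of 1.00, although all shared error has gone. This stands. The SD is not inflated by shared error, so it does not reverse, but it cannot see that error. Only a reference FAC could, and the plan has none.

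A second reply is that the direction depends on a correlation about which the documents say nothing, and that the examples hold reader error nearly constant although the plan's premise is that it falls. This also stands as a limit. A reader might infer that removing artefact must lower the ICC. The documents do not support that: it depends on how the artefact varies and relates to true FAC, and a fall in reader error from 6 to 4 points leaves only an 8% chance of a lower ICC in the simulation.

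Third, the consequence is bounded. The Outcomes section defines improvement by the numeric score, Method #2 is an added assessment, and no decision hangs on an ICC threshold. This is correct, and Method #1 is untouched. It does not make a change in ICC interpretable.

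**Conclusion.** The point holds in conditional form. With the ICC as the only measure, Method #2 can show no change or a fall when reader error has improved. This requires shared image error that varies between patients and is not negatively correlated with true FAC strongly enough to cancel its own variance (A² + 2cov > 0). It also requires that the drop in reader error does not exceed the break-even value. The documents give no FAC variances, so the size in this study cannot be computed; the figures show only what is possible under the assumed values.

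This does not show that the ICCs obtained did move the wrong way, nor that the conclusions from the impression scores fail. It does show that the direction of an ICC change is not by itself evidence about image quality. The within-image SD measures the reproducibility that Method #2 names, and is worth adding for that reason.

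**What to change.** For LV FAC and RV FAC, report the within-image reading SD in FAC points before suctioning, after suctioning, and as the after/before ratio. Give the ratio a bootstrap interval that resamples patients and keeps each patient's before and after readings together. Do this for readers A, B and C, and for investigator C's two readings.

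State whether systematic differences are included, matching each ICC. To match the consistency ICC, leave out mean differences between readers (the square root of the residual mean square). To match the absolute-agreement ICC, include the difference between C's two sessions (the square root of residual plus session variance).

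Show the between-patient variance and the ICC beside each SD, so that a reader can see which component moved. Add two sentences of interpretation: that a change in ICC alone is not read as a change in image quality, and that neither the ICC nor the reading SD detects error shared by all readers, which would need a reference FAC.

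No new readings are needed, since the SDs come from the same ANOVA as the ICCs. The plan describes the analyses in the past tense, so the cost is a small rerun and some added reporting as well as the change of wording.

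### The proportion of cases improved, reported without the proportion worsened, cannot show that suctioning improved the images, and the reader error behind it is not assessed

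*Combined protocol and SAP*

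**What the plan says.** Under Image quality assessment, method #1 is a subjective 1-5 score: "the investigators categorized the quality of all acquired images on a numeric scale based on each investigator's impression". Seven views are designated, each acquired before and after suctioning. The same section says that three investigators "assessed the quality of all TEE images post hoc", and goes on directly to say that "50 x 3 sets of images for each were evaluated to determine the interobserver variability". After 6 to 8 months, "investigator C again analyzed all images to determine the intraobserver variability". All readers were blinded to the hypothesis and to whether an image came before or after suctioning.

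Under Outcomes, "Image quality improvement was defined as an increase in this number". No minimum change is set.

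Under Statistical Analysis, the score appears twice. The first is a summary that the plan labels descriptive: "The proportion of cases showing improvement using the numeric scale". The second is a correlation of the score change, averaged within a case, with suctioned volume. Agreement statistics are confined to method #2: "Intraobserver and interobserver reliability analyses of the LV FAC and RV FAC were performed using the" ICC. The section lists paired t-tests in general terms but does not assign one to the score. No outcome is named as primary.

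**The concern.** Three things are missing around a proportion that readers will naturally take as evidence of benefit.

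- **No opposite count.** Any increase counts as improvement, but decreases and ties are not reported. A noisy ordinal score moves up and down by chance, and counting only the upward moves gives a positive figure even when nothing has changed.
- **No combination rule.** Each case yields 7 x 3 = 21 before/after differences. The plan does not say how these become one improved or not-improved case. Averaging is stated only for the correlation with volume.
- **No measure of reader error for this score.** Interobserver variability is given as a purpose of the three readers' assessments, yet only LV FAC and RV FAC, which use two of the seven views, get an agreement analysis. The most subjective measure, and the only one that covers all seven views, gets none.

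At stake is whether the reported proportion says anything about suctioning or mainly reflects chance differences between two readings.

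**Working it through.** **Inputs from the plan:** 50 cases, 7 views, 3 readers, scores 1 to 5, blinded reading, improvement = any increase. The plan gives no sample size calculation, effect size or agreement value, so there is no figure of its own to reproduce.

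**Step 1: algebra, no distributional model.** Take one reader and an image pair with no true difference. Because the reader is blinded, error is equally likely in either direction, so P(increase) = P(decrease). These two and P(tie) sum to 1, and P(tie) is the exact agreement between the two readings. Hence

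P(increase | no change) = (1 - exact agreement)/2.

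| Exact agreement | Scored as improved | Scored as worse |
|---|---|---|
| 50% | 25% | 25% |
| 60% | 20% | 20% |
| 70% | 15% | 15% |
| 80% | 10% | 10% |
| 90% | 5% | 5% |

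**Step 2: simulation of the whole case.** Assumptions that are not in the documents: latent quality normal with mean 3.3 and SD 0.8, single-reader ICC 0.4 to 0.9, independent reader errors, scores rounded and limited to 1-5, no true change. Error variance = 0.64 x (1 - ICC)/ICC. There were 4,000 runs of 50 cases x 7 views x 3 readers.

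| ICC | Exact agreement | One reader up | Mean of 3 readers up (one view) | Case mean up (21 differences) | Type I error, paired t on case means |
|---|---|---|---|---|---|
| 0.4 | 30.9% | 34.6% | 41.1% | 46.6% | 4.3% |
| 0.5 | 35.5% | 32.2% | 39.6% | 46.2% | 5.1% |
| 0.6 | 41.2% | 29.4% | 37.9% | 45.6% | 4.7% |
| 0.7 | 48.3% | 25.9% | 35.9% | 44.8% | 6.0% |
| 0.8 | 57.5% | 21.2% | 32.7% | 43.7% | 4.9% |
| 0.9 | 70.5% | 14.8% | 25.7% | 42.1% | 5.1% |

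The algebra and the simulation agree: at ICC 0.9, (1 - 0.705)/2 = 14.75%, against 14.8% simulated.

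**Step 3: reading the table.**
- If a case counts as improved when its mean change is above zero, 42.1% to 46.6% improve with no effect. In 50 cases that is 0.421 x 50 = 21 to 0.466 x 50 = 23.
- By symmetry the same share worsens, which leaves 100 - 2 x 46.6 = 6.8% to 100 - 2 x 42.1 = 15.8% exactly unchanged.
- The choice of rule matters. At ICC 0.8 the no-effect figure is 21% for one reader on one view, 33% for the mean of three readers on one view, and 44% for the case mean.
- A two-sided paired test on case means keeps its error rate at about 4% to 6%.

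**The case against.** The strongest reply is that the plan blinds its readers. This is correct and it limits the point. Symmetric error does not push the mean change towards improvement, and a paired before/after comparison of the score is not biased by it. But symmetry protects a difference or a test. It does not protect a proportion improved that is shown without its counterpart, and the plan assigns no paired test to the score.

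Four stronger readings are tempting and are not supported.

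- *The score carries the main result.* The study title and the definition of improvement make it central, but no outcome is designated primary and the proportion is labelled descriptive.
- *The missing agreement analysis is why noise counts as improvement.* The any-increase rule and the absent count of worsened cases do that. A kappa or ICC would measure the noise without removing it. The case-mean figure moves only from 42% to 47% over the whole ICC range, so it argues for the opposite count rather than for a reliability analysis.
- *Investigator C's second reading already supplies repeat scores.* The plan says that C analysed and measured the images twice, but not that the 1-5 score was given again. Repeat scores may not exist.
- *The proportion improved could be benchmarked against C's re-reading.* Even if those scores exist, a single reader's rate is not comparable with a result combined over three readers, as the columns of the table show, and drift over 6 to 8 months could distort it.

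It is also fair to say that the simulated percentages rest on chosen inputs. The algebra does not need them, but it does need an exact agreement figure, which the plan does not provide.

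**Conclusion.** The point holds as a limitation of a descriptive outcome, not as a bias in the study. As planned, the proportion improved cannot by itself show that suctioning improved the images, because a substantial proportion is expected with no effect at all: half of one minus exact agreement for a single reader and view, and about 42% to 47% of cases if the case mean is used. The first figure rests only on symmetric error, which blinding supports. The second rests on the assumed latent mean, SD, ICC range and independent reader errors.

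Separately, the size of the reader error in the score will not be known, because agreement is planned only for LV FAC and RV FAC. The three readers' scores needed to assess it are documented as collected. The plan should be changed, but the gap does not invalidate the study.

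**What to change.** 1. **Report all three directions under one rule.** State one combination of the three readers in advance, for example the mean score, which fits the averaging that Statistical Analysis already uses for the volume correlation. For each view and for each case, report improved, unchanged and worsened together.
2. **Test the paired change.** Compare the combined score before and after within patient, for example with a signed-rank test, at the plan's existing threshold ("A p-value of less than 0.05 was considered statistically significant").
3. **Assess agreement for the score.** For each view, report quadratic-weighted kappa or absolute-agreement ICC across readers A, B and C. Do the same for investigator C's two readings only if the score was in fact repeated, and state whether it was.

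The first two items settle how the result is interpreted. The third shows how large the reader error is. Steady differences in level between readers lower absolute agreement but cancel in each reader's own before/after change, so the between-reader figure is only an indirect guide to the chance rate of increases.

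The cost is some analysis wording and R code on scores already held, with no new readings. The downside is a little more analysis and a less favourable headline figure, since worsened cases will stand beside improved ones.

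### The inter-reader ICC for LV FAC and RV FAC is a consistency coefficient, so constant differences between readers drop out and agreement is overstated wherever they exist

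*Combined protocol and SAP*

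**What the plan says.** Under Image quality assessment, method #2 takes FAC reproducibility as a stand-in for image quality, "assuming that better TG Mid SAX and ME4C image quality would yield better LV FAC and RV FAC reproducibility, respectively". Three certified echocardiographers (A, B and C) "assessed the quality of all TEE images post hoc", and the section adds: "Thus, 50 x 3 sets of images for each were evaluated to determine the interobserver variability". For the repeat reading, "following an interval of between 6 and 8 months, investigator C again analyzed all images to determine the intraobserver variability".

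Under Statistical Analysis, "Intraobserver and interobserver reliability analyses of the LV FAC and RV FAC were performed using the ICC", and the type of coefficient is then named: "We obtained consistency ICCs for interobserver variability using all three investigators and absolute-agreement ICCs for intraobserver variability using investigator C".

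The plan gives no reason in its text for using two definitions. It does not say whether the ICCs are single- or average-measure, whether confidence intervals are reported, or how the ICCs before and after suction are to be compared. It plans no absolute-agreement ICC between readers, no Bland-Altman analysis and no estimate of reader bias.

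**The concern.** FAC is a measured percentage. In the ordinary sense, two readers reproduce each other's FAC if they obtain the same value, not merely if their values rise and fall together. A consistency ICC asks only the second question. If one reader traced every ventricle 8 FAC points below another, it would be unchanged.

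Two things are at stake. First, the reported inter-reader figure can make the readers look more interchangeable than they are. Second, method #2 exists to show whether suction improves reproducibility. If part of that improvement takes the form of readers' average values moving closer together, the planned coefficient does not register that part.

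The plan applies the stricter definition to one reader compared with herself or himself. It applies the looser one to three different readers, where a systematic offset is a natural possibility.

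**Working it through.** **Plan's own figure.** There is none to reproduce: the documents give no ICC value, no FAC variance components and no sample-size calculation.

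**Inputs from the documents.** Three readers, all reading all images. 50 image sets per reader, read here as 50 patients. Consistency ICC between readers; absolute-agreement ICC within investigator C.

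**Inputs assumed for illustration.** Between-patient FAC SD 10 points (Vb = 100). Residual SD 5 points (Ve = 25). Reader offsets of -d, 0, +d points, whose sample variance is Vr = 2d²/2 = d².

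**Formulas (single measure).**
- Consistency: Vb / (Vb + Ve)
- Absolute agreement: Vb / (Vb + Vr + Ve)

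**Closed form.** Consistency is 100/125 = 0.80 for every d. Absolute agreement is:
- d = 0: 100/125 = 0.80
- d = 3: 100/(100 + 9 + 25) = 100/134 = 0.75
- d = 5: 100/(100 + 25 + 25) = 100/150 = 0.67

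**What each coefficient registers.** Mean ICCs from a simulation with 50 patients, three readers and 4000 runs:

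| Situation | Consistency | Absolute agreement |
|---|---|---|
| A. Offsets of ±5 before suction, none after; residual SD 5 throughout | 0.79 to 0.79 | 0.66 to 0.79 |
| B. No offsets; extra image-specific error of SD 5 before suction, none after | 0.66 to 0.79 | 0.66 to 0.79 |
| C. Offsets of ±5 at both times; residual SD 7.07 before, 5 after | 0.66 to 0.79 | 0.56 to 0.66 |
| D. Offsets of ±10 in about half the images (one time point) | 0.64 | 0.54 |

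The simulated means lie slightly below the closed-form values (0.79 against 0.80) because of small-sample bias.

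In A, the readers' convergence is invisible to the planned coefficient. In B, both coefficients see the change equally. In C, both rise, and consistency is higher at each time. In D, consistency falls below the 0.79 seen without offsets, so an offset confined to some images is partly detected.

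**Within investigator C.** A shift of 0, 5 or 10 points between the two reading sessions gives absolute-agreement ICCs of 0.79, 0.72 and 0.57. That coefficient does register a systematic shift, but only within one reader.

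**The case against.** A reader might infer that method #2 as a whole cannot see the main way in which poor images degrade FAC. The documents do not support this:

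- Only the average, constant offset between readers is removed. Image-specific disagreement and random tracing error still lower the consistency ICC (B and C).
- If readers fall back on personal habit where borders are poorly seen, and border visibility differs between images, much of the effect is reader-by-image disagreement, which the consistency ICC does reflect (D).
- Nothing in the documents shows that systematic offset is a main effect of poor image quality.

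A reader might also infer a large hidden gain. With offsets narrowing from ±8 to ±3, absolute agreement would go from 100/(100 + 64 + 25) = 0.53 to 0.75 while consistency stayed at 0.80. That assumes a 16-point spread among three certified readers, and that suction narrows the offsets without reducing random error. Neither has a basis in the documents.

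Three further points stand. The same readers read all images, and "all investigators were blinded to which images were obtained before or after suctioning", so an offset equal at both times changes the level of the ICC but need not change the direction of the contrast. Consistency is a recognised choice for a fixed panel of readers, and the plan cites ICC references that were not available here, so a rationale in them cannot be excluded. The plan also nowhere sets out to compare the inter-reader ICC with the intra-reader one, so the mismatch of definitions does not invalidate a planned comparison.

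These points limit the reach of the concern. They do not supply the missing information: no planned analysis shows how far the three readers differ systematically.

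**Conclusion.** The point holds in a limited form. The planned inter-reader ICC ignores constant additive reader differences, overstates agreement in FAC values when those exist, and misses a before/after change to the extent that it consists of average offsets converging. The other forms of disagreement remain visible to it.

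The size cannot be determined from the documents. Under the assumed SDs of 10 and 5 points, the overstatement is nil with no offset, about 0.05 with ±3 (0.80 - 0.75) and about 0.13 with ±5 (0.80 - 0.67). Different SDs would give different gaps. The direction is firm in expectation. In a given sample, the agreement ICC can come out slightly above consistency when the reader mean square is smaller than the error mean square.

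**What to change.** In the Statistical Analysis section:

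1. Make the two-way absolute-agreement, single-rater ICC the main inter-reader coefficient for LV FAC and RV FAC.
2. Report it separately before and after suction, with confidence intervals. In situation A above, the sampling SD of a single ICC was about 0.04 to 0.06, so point estimates alone could mislead.
3. Keep the consistency ICC as a secondary figure, so that the gap between the two shows systematic reader offset. Each reader's mean FAC would show the offset directly.
4. State the model and the single- or average-measure form for the intra-reader ICC as well. The plan says only that it is absolute-agreement.

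Cost: a different option in the ICC call and a few sentences of text. All three readers already read all images, so no new data are needed. The reported inter-reader ICC may be lower. With three readers, the between-reader variance rests on 3 - 1 = 2 degrees of freedom, so the interval for the agreement ICC may be wide. If the gap proves negligible, nothing is lost.
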